**Investigational Product, Dosage, and Mode of Administration:**

Dalantercept is a frozen liquid formulation at a concentration of 50 mg/mL in 10 mM Tris buffered saline (pH 7.5 ± 0.5). Dalantercept will be administered by subcutaneous (SC) injection(s) once every 3 weeks until progression of disease or unmanageable toxicity occurs. The dose level of dalantercept for the first cohort will be 0.6 mg/kg SC q3 weeks, plus a starting dose level of axitinib 5 mg PO BID. The planned dose escalation for dalantercept is below.

**Part 1:**

**Dose Level Per Cohort**

Dose Cohort	Dalantercept Dose Level (mg/kg)	Number of Patients
1	0.6	3-6
2	0.9	3-6
3	1.2	3-6
4	1.5	3-6
Expansion Cohort	TBD	up to 20
Total (planned)		up to 44

**Part 2:**

Patients will be randomized to receive dalantercept or placebo plus a starting dose of axitinib 5 mg PO BID. Based upon a safety review of the Part 1 data, the recommended Phase 2 dose level of dalantercept was determined to be 0.9 mg/kg in combination with axitinib.

Please refer to the Inlyta® (axitinib) prescribing information, *Dosage and Administration*, for how axitinib is supplied.

**Safety Assessment: Dose Escalation**

**Dose-Limiting Toxicity (DLT) Definition:**

A DLT is defined as any of the following events that are considered possibly or probably related to dalantercept.

- Weight gain (due to fluid retention) grade 2 or higher
- Pulmonary edema grade 2 or higher
- Bleeding grade 2 or higher
- Cardiovascular event grade 3 or higher
- Non-hematologic adverse event grade 3 or higher with the exception of grade 3 or higher amylase and lipase in the absence of clinical symptoms and grade 3 nausea, vomiting, or diarrhea in the absence of appropriate prophylaxis
- Grade 3 thrombocytopenia with associated bleeding

- Grade 4 anemia or thrombocytopenia
- Grade 4 neutropenia with fever

**Part 1:**

Safety and Dose Limiting Toxicities (DLTs) will be evaluated by the SRT. In addition, the MTD or maximum tested dose, the number of patients to be enrolled in the expansion cohort and the recommended Phase 2 dose level for Part 2 will be determined by the SRT. The SRT, which is comprised of a minimum of one study investigator, a Sponsor medical monitor, and a clinical investigator not participating in this study, will review safety data including AEs and serious adverse events (SAEs), laboratory results (including hematology and chemistry) and vital signs data through study day 29 to assess the safety of a dose level prior to dose escalation. Dose escalation will not occur until the patients in the preceding dose level have been evaluated for a minimum of 29 days.

After a minimum of 3 evaluable patients have been evaluated for a minimum of 29 days, the SRT will consider dose escalation to the next dose level cohort or the addition of 3 additional patients to the current dose cohort based in part upon the following dose escalation criteria:

- If there are no DLTs, dose escalation to the subsequent dose level may proceed.
- If 1 of 3 patients at a dose level experiences a DLT, 3 additional patients may be enrolled at the current dose level.
  - If there are no further DLTs in the 3 additional patients, dose escalation to the next dose level may proceed.
- If a DLT occurs in  $\geq 2$  patients in any dose level cohort of 3-6 patients, no further dose escalation will occur and a previous or lower intermediate dose level will be defined as the MTD. Patients enrolled in this dose level cohort may continue to receive additional doses of dalantercept plus axitinib at an appropriate dose level as outlined in the Management of Adverse Events table.

**Expansion Cohort:**

Once the MTD or maximum tested dose level has been determined by the SRT and Sponsor, up to a total of 20 patients may be enrolled at up to 2 different dose levels at or below the MTD to further evaluate safety, tolerability, and preliminary anti-tumor activity of dalantercept plus axitinib and to determine the recommended Phase 2 dose level for Part 2. The SRT will meet after a minimum of 10 patients have been evaluated for a minimum of 29 days to review safety data and vital signs data to assess safety.

If 4 DLT events occur at any time during the first 29 days in a minimum of 10 patients in the expansion cohort, further enrollment in that expansion cohort will be discontinued. The SRT may decide to cease enrollment if fewer than 4 DLT event(s) occur if the nature of the event(s) is deemed a significant risk to patients for that dose level. The next lower or an intermediate dose level may be recommended to enroll up to an additional 10 patients for assessment of safety following the same stopping rules.

**Part 2:**

The sponsor and an independent data monitoring committee (DMC) are responsible for reviewing safety throughout Part 2 of the study. The DMC will be comprised of a minimum of 3 members (non-Sponsor and non-study investigators) and will review available study data (e.g. serious

adverse events (SAEs), adverse events (AEs), laboratory results (including hematology and chemistry), ECHO, ECG, tumor response assessment scans and vital signs data) on a regular basis to assess the safety of the patients and verify the proper conduct of the trial. The DMC responsibilities, membership, meeting frequency, and procedures will be outlined in a separate DMC charter.

**Assessments for Evaluation:**

**Efficacy:** Response to treatment with dalantercept plus axitinib will be determined according to the Response Evaluation Criteria in Solid Tumors (RECIST, version 1.1, [Appendix 1](#)) for patients with solid tumors. Patients will be assessed for efficacy using data from tumor response assessments (PFS, ORR, DR and DCR) as well as evaluation of OS and PD biomarkers.

**Safety:** Patient safety will be assessed by monitoring AEs using the current active minor version of the NCI-CTCAE v4, clinical laboratory tests, ECHO, ECG, vital signs (including weight), physical examinations, and ADA testing.

**Statistical Methods:**

**Sample Size Calculation:**

**Part 1**

There is no formal sample size calculation for Part 1 (dose escalation and expansion).

**Part 2**

The primary analysis of efficacy will be performed when at least 82 PFS events have been observed and documented. If the median time to PFS is assumed to be 5 months in the placebo plus axitinib control group, then a total of 82 PFS events will provide approximately 80% power to detect a 3 month extension from 5 to 8 months in the dalantercept plus axitinib experimental treatment group when performing a stratified log-rank test of the null hypothesis of no difference between treatment groups using a one-sided 10% significance level.

The projection of power is made under a proportional hazards assumption so that the hazard ratio (HR) for dalantercept plus axitinib relative to placebo plus axitinib is equal to 0.625 under the alternative hypothesis. It is projected that 130 patients will need to be randomized to obtain 82 PFS events. The number of patients to be randomized provides for patient censoring patterns that could occur under the alternative hypothesis in the event the dropout rate is higher than expected in either treatment group.

**Analysis Populations:**

The **All Treated (AT) Population** includes all patients who received any study drug. The AT is the population that will be used when performing the primary analysis of the primary endpoint and all safety analyses. The AT population will be analyzed according to treatment received.

The **Full Analysis Set (FAS)** includes all randomized patients. The intent-to-treat principle will be used for this study population. The FAS will be used in secondary analyses of the primary endpoint.

The **Pharmacokinetics (PK) population** will consist of all patients who received at least 1 dose of dalantercept and axitinib and have sufficient PK samples collected and assayed.

**Statistical Analysis:**

Details regarding the final data analysis will be discussed in a separate Statistical Analysis Plan (SAP).

The primary analysis of PFS will be based on investigator assessment using the AT population. Time to radiographic progression or death is the primary efficacy analysis and will be performed using a stratified (by prior treatment) log-rank test.

A log-rank test stratified by prior mTOR and immune therapy will be used to test the null hypothesis of no difference between dalantercept plus axitinib and placebo plus axitinib using a one-sided 0.10 significance level. Kaplan-Meier curves will be displayed depicting each treatment group. The hazard ratio (dalantercept plus axitinib: placebo plus axitinib) will be estimated using a stratified Cox proportional hazards model along with the 95% confidence intervals.

For the secondary PFS objective in the subgroup of patients who had 2 or more prior lines of anticancer therapy, the stratified log-rank test will be performed at one-sided 0.20 significance level due to a smaller sample size.

**Data Monitoring Committee:**

A data monitoring committee (DMC), independent from the sponsor, will be established to review unblinded safety data on a regular basis and to make appropriate recommendations regarding the conduct of the trial.

## 2. SCHEDULE OF EVENTS

Schedule of Events 												
	Screening 	Cycle 1			Cycle 2		Cycle 3	Cycle 4	Cycle 5 	Cycle 6	Final Visit 	Follow Up 
		C1D1 	C1D8	C1D15	C2D1 	C2D8	C3D1 	C4D1 	C5D1 	C6D1 		
	Day -14	Day 1	Day 8 (± 2d)	Day 15 (± 2d)	Day 22 (± 2d)	Day 29 (± 2d)	Day 43 (± 3d)	Day 64 (± 3d)	Day 85 (± 3d)	Day 106 (± 3d)		
Informed consent 	X											
Inclusion/exclusion criteria	X	X										
Medical history	X											
Archived tumor biopsy	X											
Head CT or MRI 	X											
Pregnancy test 	X	X			X		X	X	X	X		
Physical examination 	X	X	X	X	X	X	X	X	X	X	X	
Vital signs (including weight)	X	X	X	X	X	X	X	X	X	X	X	
ECOG and Karnofsky performance status	X 	X					X		X		X	
Hematology/serum chemistry 	X 	X 	X	X	X	X	X	X	X	X	X	
Thyroid Function	X 	X 					X		X 			
Urinalysis	X 	X 			X		X	X	X 		X	
PD blood biomarkers		X			X	X	X	X	X 		X	
PK blood sample collection 		X			X		X					
Anti-drug antibody (ADA)		X					X		X 		X 	X 
ECHO scan 	X 							X			X 	
ECG (12-lead) 	X							X			X 	
Chest X-ray (CXR) 	X 											
Tumor response assessment scan 	X 						X		X 		X 	X 
Monitoring of AEs and concomitant medications	X 	X 	X	X	X	X	X	X	X	X	X	
Dalantcept/placebo administration		X			X		X	X	X	X		
Axitinib administration		Continuous daily dosing (BID)										
Survival Follow-up												X 

-  Informed consent must be obtained within 28 days prior to C1D1 and prior to any study specific procedures.
-  All visit day windows should be considered relative to the date of the previous dose of dalantercept/placebo. Actual visit days (e.g., day 1, day 8, day 15) may be different than planned due to windows on visits and potential dosing delays.
-  All screening procedures should be performed within 14 days prior to study day 1. ECHO, CXR and tumor response assessment scans obtained for clinical purposes within 28 days prior to study day 1 may be used as the baseline image for this study and do not need to be repeated.
-  Head CT or MRI is required at screening to exclude any patients with active brain metastases. Head assessment scans obtained for clinical purposes within 28 days prior to study day 1 may be used as the baseline image for this study and do not need to be repeated. Scans do not need to be repeated at subsequent visits unless clinically indicated.
-  Urine or blood pregnancy test required for patients of child bearing potential only.
-  A full physical exam [skin (including telangiectasias), head, eyes, ears, nose, throat and neck, lymph nodes, cardiovascular, respiratory, gastrointestinal, and musculoskeletal (including edema)] is required at screening, C1D1, C1D8, C2D1, C3D1, C4D1, C5D1, C6D1 and the final visit. A neurologic exam is required at screening only and only repeated if clinically indicated. At all other timepoints noted and beyond C6, a targeted physical exam of the respiratory, cardiovascular and musculoskeletal (including edema) body systems is required. If clinically indicated, additional assessment of other body systems should occur.
-  Karnofsky Performance Status only required at Screening.
-  Assessments performed prior to dosing on C1D1 will be considered baseline. Baseline hematology, chemistry, and urinalysis results must be reviewed prior to dosing on C1D1 but may be collected up to 72 hours prior to dosing. Therefore if the screening visit is within 72 hours prior to study day 1, hematology, chemistry and urinalysis do not need to be repeated on C1D1. This includes the following:  
**Chemistry** - albumin, alkaline phosphatase (ALP), ALT, AST, blood urea nitrogen (BUN), calcium, chloride, carbon dioxide (CO2), creatinine, glucose, lactate dehydrogenase (LDH), phosphorus, potassium, sodium, total bilirubin, amylase, and lipase. After C15, amylase and lipase are not required unless clinically indicated.  
**Hematology** - complete blood count (CBC) with differential; CBC includes RBCs, white blood cells (WBCs), platelets, hemoglobin, hematocrit, mean corpuscular volume (MCV), mean corpuscular hemoglobin (MCH), mean corpuscular hemoglobin concentration (MCHC). PT/INR and aPTT should be collected at screening only (within 14 days of study day 1)  
**Urine by urinalysis or dipstick analysis** - pH, specific gravity, protein, glucose, ketones, blood, leukocyte esterase, and nitrite with microscopic examination if indicated.
-  Baseline thyroid function may be collected up to 72 hours prior to dosing. If the screening visit is within 72 hours of study day 1, thyroid function does not need to be repeated. This includes the following: free thyroxine (T4) and thyroid stimulating hormone (TSH).
-  ECHO scans for ejection fraction and presence or absence of pericardial effusion only. MUGA should be performed to estimate EF if quality of ECHO is not good. Additional testing to be done if clinically indicated. ECHO scans may be performed up to 5 days prior to a scheduled visit. A complete cardiac evaluation including CXR, ECG, and ECHO should be performed if determined to be clinically necessary even if it is an unscheduled time point. Cardiac evaluation should be included at the final visit for early termination patients if determined to be clinically necessary.
-  Perform all assessments prior to dosing dalantercept/placebo and review for potential dose modifications. All AEs and abnormal laboratory or other findings that might require modification of dosing (see [Section 10.6](#)) should be reviewed prior to dosing to ensure that the patient is still eligible to receive dalantercept/placebo. Assessments performed on Cycle 1 Day 1 (C1D1) prior to dosing will be considered baseline.

- Tumor response assessment scans may be performed up to 5 days prior to a scheduled visit (except screening & final visit which have wider windows). Tumor response assessment scans should be reviewed prior to dosing the next cycle of treatment. Tumor response assessment scans should be performed every 6 weeks regardless of dalantercept/placebo or axitinib dosing delays through C15. After C15 tumor response assessment scans should be performed every 12 weeks regardless of dalantercept/placebo or axitinib dosing delays (e.g. C19D1, C23D1, etc).
- Concomitant medications taken within 28 days prior to study day 1 will be collected.
- Adverse events will be collected after the first dose administration. Non-serious AEs prior to dosing on study day 1 will be collected as medical history.
- PK blood sample collection should be performed pre-dose for dalantercept/placebo and axitinib at C1D1, C2D1 and C3D1. C3D1
- If the patient has stable or responding disease at the end of 6 cycles of treatment, repeat the procedures performed for cycles 5 and 6 until the patient is taken off study (C7D1=C5D1, C8D1=C6D1, etc.). NOTE: After C5, ADA, urinalysis, thyroid function and PD biomarkers only need to be repeated once every 4 cycles (C9D1, C13D1, etc).
- Patients who terminate from the study should complete the final visit. The final visit should occur approximately 30 days after the last dose of dalantercept/placebo  $\pm$  10 days. The tumor response assessment scans at the final visit should only be performed to assess progression if progression has not already been confirmed by a previous tumor response assessment scan.
- If the patient has a positive ADA result at their last assessment, the patient may be asked to return approximately every three months for additional testing, until a negative result is obtained or the result is considered stabilized.
- All patients should be contacted every 3 months ( $\pm$  2 weeks) from the date of the final visit for survival. Patients will also be asked to return to the clinic approximately once every 3 months for tumor response assessment scans if progression of disease has not previously been documented. Patients that discontinue study treatment and initiate a new therapy or continue on axitinib alone, prior to documented radiographic disease progression are not required to return to the clinic every 3 months for tumor response assessment scans.

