Subcutaneous administration of dalantercept once every 3 weeks in this study was generally well tolerated. Treatment-related SAEs occurred in 5 patients including 3 patients with fluid overload and/or congestive heart failure (CHF), 1 patient with LV dysfunction, and 1 patient with fatigue. Adverse events (AEs) observed with increased frequency at higher dose levels included peripheral edema, anemia, epistaxis, and telangiectasia. The AEs of epistaxis and telangiectasia may be related to the mechanism of action of dalantercept on angiogenesis, leading to dilated vessels in the skin. Dose-dependent fluid retention manifested as peripheral edema, dyspnea, and weight gain, responded to diuretic therapy. Dalantercept treatment resulted in a dose-dependent decrease in red blood cells (RBC) and hemoglobin levels, with no evidence of hemolysis or hemorrhage. No significant, dose-related events of hypertension, GI perforation, or proteinuria have been observed in the study to date, indicating a safety profile that appears distinct from VEGF-inhibitors. Due to toxicities observed at higher doses, patients in the dose expansion cohort were treated with 1.6 mg/kg.

Dalantercept is also being evaluated in an on-going Phase 2, open-label study in patients with recurrent or metastatic squamous cell carcinoma of the head and neck (SCCHN, A041-03) who have been previously treated with at least one platinum-containing regimen. The primary objective is to estimate the objective response rate (ORR) in this population. Secondary objectives include safety and tolerability and pharmacokinetic (PK) profile of dalantercept as well as evaluate progression free survival (PFS), overall survival (OS), time to tumor progression (TTP), duration of response, and rate of disease control (ORR + stable disease [SD]). In addition, the study will explore association of the expression of BMP9/10, ALK1 and/or other

relevant markers in tumor tissue and blood with tumor response and/or other assessments of clinical response and pharmacodynamic (PD) biomarkers. The dalantercept IB should be reviewed prior to initiating the study for the most current information.

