#### 11.2.2. Other Safety Assessments

Specific details regarding any testing to be performed by a central laboratory for this study will be located in the Study Reference Guide.

- Physical examination: Full exam [skin (including telangiectasias), head, eyes, ears, nose, throat and neck, lymph nodes, cardiovascular, respiratory, gastrointestinal, and musculoskeletal (including edema)] required at screening, Cycle 1 Day 1 (C1D1), C1D8, C2D1, C3D1, C4D1, C5D1, C6D1 and the final visit. A neurologic exam is required at screening and repeated only if clinically indicated. At all other timepoints noted and beyond C6, a targeted exam of the respiratory, cardiovascular and musculoskeletal (including edema) is required. If clinically indicated, additional assessment of other body systems should occur. Findings at screening and prior to dosing on C1D1 will be recorded on the medical history form. Findings after C1D1 dosing will be recorded as AEs.

- Vital signs: Including height, weight, systolic and diastolic BP, temperature (documented in degrees Celsius), respiration rate, and heart rate. Height will be collected at screening only.
- Cardiac function testing: 12-lead ECG and ECHO scan (Ejection Fraction and presence or absence of pericardial effusion). MUGA should be performed to estimate EF if quality of ECHO is not good.
- Anti-drug antibody and neutralizing antibody testing: As indicated.

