### **12.2. Dosing Days and Interim Visits**

- All screening and study day 1 procedure results required to confirm eligibility must be obtained and reviewed prior to study drug administration. Patient eligibility for inclusion/exclusion criteria must be confirmed from these results, as applicable. Ideally, patients should be randomized within 48 hours of C1D1.
- Baseline hematology, chemistry, and urinalysis results must be reviewed prior to dosing on C1D1 but may be collected up to 72 hours prior to dosing. Baseline thyroid function may also be collected up to 72 hours prior to dosing. Therefore if the screening visit occurs within 72 hours of study day 1, the hematology, chemistry, thyroid function and urinalysis testing do not need to be repeated.
- Any non-serious AEs that occur prior to dosing in cycle 1 should be recorded in the medical history section of the CRF.
- All AEs that occur after dosing in cycle 1 should be recorded in the AE page of the CRF.

- On subsequent dosing days, all AEs and abnormal laboratory or other findings that might require modification of dosing (see [Section 10.6](#)) should be reviewed prior to dosing to ensure that the patient is still eligible to receive additional doses of dalantercept/placebo. Please note that there is an extended window of up to 5 days for the ECHO and tumor response assessment scan, when required.
- PK blood sample collection should be performed pre-dose for dalantercept/placebo and axitinib at C1D1, C2D1 and C3D1.
- Tumor response assessment scans should be performed every 6 weeks regardless of dalantercept/placebo or axitinib dosing delays through C15. After C15 tumor response assessment scans should be performed every 12 weeks regardless of dalantercept/placebo or axitinib dosing delays (e.g. C19D1, C23D1, etc.).
- The schedule of events outlines procedures through C6D1. If patients have stable or responding disease and are able to continue beyond 6 cycles of treatment, the procedures outlined for cycle 5 and 6 should be repeated until the patient comes off study (i.e. C7D1=C5D1, C8D1=C6D1, etc.). The only exception is that after cycle 5, ADA, urinalysis, thyroid function and PD biomarkers are required once every 4 cycles instead of once every 2 cycles (i.e., C9D1, C13D1, etc.).

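### The rules for the physical exam after cycle 6 conflict, and under the more specific rule no skin exam is required from C6D1 until the final visit, so late telangiectasia is not systematically looked for

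*Combined protocol and SAP*

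**What the plan says.** Four places govern the physical exam at later visits.

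- **Schedule of Events, footnote 6.** The full exam opens with the skin: "A full physical exam [skin (including telangiectasias), head, eyes, ears, nose, throat and neck, lymph nodes". It is required at screening, C1D1, C1D8, day 1 of cycles 2 to 6, and the final visit. Elsewhere the exam is reduced: "At all other timepoints noted and beyond C6, a targeted physical exam of the respiratory, cardiovascular and musculoskeletal (including edema) body systems is required". A fallback follows: "If clinically indicated, additional assessment of other body systems should occur".
- **Section 11.2.2.** It gives the same split: "At all other timepoints noted and beyond C6, a targeted exam of the respiratory, cardiovascular and musculoskeletal (including edema) is required". It also says that exam findings after the first dose are recorded as adverse events.
- **Schedule of Events, footnote 16.** For patients who continue past cycle 6, sites are to "repeat the procedures performed for cycles 5 and 6 until the patient is taken off study", with C7D1 equated to C5D1 and C8D1 to C6D1. A note relaxes ADA, urinalysis, thyroid function and PD biomarkers.
- **Section 12.2.** It says that "the procedures outlined for cycle 5 and 6 should be repeated until the patient comes off study", and adds: "The only exception is that after cycle 5, ADA, urinalysis, thyroid function and PD biomarkers are required once every 4 cycles".

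On why the skin matters, Section 7.3 reports: "Adverse events (AEs) observed with increased frequency at higher dose levels included peripheral edema, anemia, epistaxis, and telangiectasia". The same section says that epistaxis and telangiectasia may be related to the drug's mechanism. Section 7.4 lists telangiectasia among the events seen in at least 10% of patients in the monotherapy trials and connects it with the inherited ALK1-deficiency phenotype.

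**The concern.** C5D1 and C6D1 both carry the full exam. Read literally, Section 12.2 therefore continues the full exam, skin included, at every later cycle. Footnote 6 and Section 11.2.2 say that it stops. The text does not say which prevails.

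Under footnote 6 and Section 11.2.2, the last required on-treatment look at the skin is at C6D1, and the next is at the final visit, about 30 days after the last dose. In between, the plan does not require anyone to look for an event that it describes as dose-related and possibly mechanism-linked. Exam findings become adverse events, and Section 15.4.2 tabulates adverse event incidence by preferred term and grade in support of the Part 2 safety objective. A lesion that appears late and fades before the final visit could go unrecorded. One first seen at the final visit could be given a late onset date.

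**Working it through.** **1. The texts side by side**

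| Visit | Footnote 6 and Section 11.2.2 | Footnote 16 and Section 12.2, read literally |
|---|---|---|
| C5D1, C6D1 | Full exam, skin included | Full exam, skin included |
| C7D1 onward | Respiratory, cardiovascular, musculoskeletal; others if indicated | Same as C5D1/C6D1, so full exam |
| Final visit | Full exam, skin included | Not addressed by the repeat rule |

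The exception in Section 12.2 covers ADA, urinalysis, thyroid function and PD biomarkers. The physical exam is not among them.

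**2. Which reading is more natural.** Footnote 6 and Section 11.2.2 address visits beyond cycle 6 expressly, and they agree. The rule in footnote 16 and Section 12.2 is general. Section 12.2's claim to a single exception is also inexact on its own terms: the same section moves tumor scans from every 6 to every 12 weeks after C15, and footnote 8 and Section 11.2.1 drop routine amylase and lipase after C15. The specific rule is therefore the likelier one in practice, and it is the one that leaves the gap.

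**3. How much treatment time the gap covers.** The plan gives no figure, so this is an illustration.

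Inputs:
- C6D1 is Day 106 (Schedule of Events), which is 105 days after Day 1: 105 / 30.4375 = 3.45 months.
- C7D1 is three weeks later: 126 / 30.4375 = 4.14 months.
- Design PFS medians are 5 and 8 months (Section 15.2).
- Assumption: time on treatment is exponential with median m, with PFS standing in for time on treatment.

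For an exponential time with rate λ = ln 2 / m, expected time after c is exp(−λc)/λ and total expected time is 1/λ. The share after c is therefore exp(−λc) = 2^(−c/m).

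| Median m (months) | Share after C6D1 (c = 3.45) | Share after C7D1 (c = 4.14) |
|---|---|---|
| 3 | 45% | 38% |
| 5 (control, design) | 2^(−0.690) = 62% | 56% |
| 8 (experimental, design) | 2^(−0.431) = 74% | 70% |
| 12 | 82% | 79% |

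C6D1 is the last required on-treatment skin exam under footnote 6; C7D1 is the first visit that has only the targeted exam. Under the literal reading of Section 12.2 the share of treatment time without a required skin exam at each cycle is 0%.

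**The case against.** The strongest reply is that the four places can be read together. The schedule row being repeated is the physical exam with its footnote, and that footnote already says what the exam consists of after cycle 6. The exception in Section 12.2 concerns how often tests are done (every 4 cycles rather than every 2), whereas the exam keeps its frequency and changes only in content. This largely stands as an account of what was intended, and footnote 16 itself makes no claim to a sole exception. It does not close the point, because the harmonised reading is exactly the one that ends the required skin exam.

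A second reply is that other routes of capture remain. Adverse events are monitored at every visit through open questions, spontaneous reports, observation and examination (Section 14.5), and the skin may be examined if indicated. This also stands. A reader might infer that late cases are lost unless the patient volunteers them; the documents do not support that. What is missing is a routine look.

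A reader might also infer that telangiectasia is ascertained differently from site to site. No passage assigns different rules to sites. With about 60 centers and conflicting text it is a possible consequence, but if every site follows one rule there is no such difference.

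Finally, the targeted list fits the fluid overload and cardiac concerns in the earlier data, the same blinded schedule applies to both arms, and Section 15.4.2 plans no time-to-onset analysis. These limit the consequence. A lesion still present at the final visit would count toward incidence. Adding nose and throat would gain little, since epistaxis is a symptom that patients can report.

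**Conclusion.** The texts conflict and must be reconciled. Under footnote 6 and Section 11.2.2, the more specific rule, late telangiectasia is not systematically looked for between C6D1 and the final visit.

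If time on treatment follows the design PFS medians, about 62% to 74% of it falls in that interval, and 45% to 82% for medians of 3 to 12 months. Part 2 treatment also ends when either drug is stopped, so time on treatment may be shorter than PFS, which points to the lower part of the range. These are shares of treatment time without a required skin exam; they do not estimate missed cases. If dalantercept lengthens treatment as hypothesised, the larger share falls in that arm, although the rule is the same for both.

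The consequence is possible under-ascertainment of late telangiectasia in the safety description. The primary PFS analysis is untouched. The change is worth making because it is specific and cheap.

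**What to change.** Add skin, with telangiectasias named, to the targeted exam in Schedule of Events footnote 6 and in Section 11.2.2 for visits after cycle 6. Amend footnote 16 and Section 12.2 to refer to that exam, and reword the exception sentence in Section 12.2 so that it no longer excludes the change in the exam. All four places then describe one exam.

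The cost is protocol wording, any matching case report form wording, and a brief addition to an exam already done at each visit. No new visit is needed. If the sponsor prefers not to examine the skin routinely after cycle 6, the four places should still be aligned, and the safety report should say that telangiectasia was routinely looked for only through C6D1 and at the final visit.
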